#### [\[1\] AE and Categorical Safety only](#)

**Table 3** at Section 4.2. Immunogenicity evaluations will be assessed as shown in the Schedule of Assessments (Appendix 6.1).

Concentration below lower limit of quantification (BLQ) will be set to LLOQ/2 = 1.9 for summary calculations and graphical presentation. BLQ values will be listed as is in the source. Results of anti-S-Ab concentration will be summarized descriptively as indicated in Section 4.2.

Categorical results of anti-S-Ab, anti-N-Ab and PBMC ELISpot test will be tabulated by number and percentage of subject in each category.

Count data (micro neutralization test [titer]) will be summarized descriptively as indicated in Section 4.2.

Numeric assay result will be derived using the dilution factor from source data, ie 1:10 = 10, 1:20 = 20, etc. For result below limit of detection (LOD) which reported as <1:10 numeric result will be set to five (5) for summaries and graphical analyses.

Geometric mean titer for time point j will be calculated as

$$GMT_j = e^{\frac{\sum_{i=1}^{n_j} \ln(x_{ij})}{n_j}}$$

, where  $x_{ij}$  is the titer observed at time point j for subject i, and  $n_j$  is the number of observations at time point j.

To visualize the comparison between treatment groups the following graphs will be presented:

- Mean concentration – time profile of anti-S-Ab on semi-logarithmic scale.
- Individual concentration – time profiles (spaghetti plot) of anti-S-Ab on semi-logarithmic scale.
- By-visit combined plots (box + scatter) for micro neutralization and PBMC ELISpot results.

Inclusion of subjects for ELISpot analyses will depend on validity of the negative control results and be decided on case by case basis. Specifically, for the IFN $\gamma$  ELISpot test on fresh PBMC at week 2, number of pools with positive results obtained in PBMC ELISpot test will be assigned into two categories such as negative or positive. Result will be negative if number of positive pools is zero and positive if number of positive is greater than or equal to one.

ELISpot assay results on frozen PBMC samples obtained on Week 2, will be provided by the sponsor (outside of EDC system used in the study) and will be analyzed with other assay results recorded in EDC.

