10.2. Statistics analysis

This is a descriptive safety study, where participants will be vaccinated with different doses of GRAd-COV2 against SARS-CoV-2. Forty-five participants per age cohort (for a total of 90 subjects) will be vaccinated in total. This sample size should allow an estimation to be made of the frequency and magnitude of outcome measures, rather than aiming to obtain formal statistical significance for differences between groups.

Safety data will be presented according to frequency, severity and duration of adverse events. The primary analysis for immunogenicity will be to assess the difference in magnitude of SARS-CoV-2 specific T-cell and antibody responses between the groups. We will assess vaccine immunogenicity by comparing the change in these immunological parameters from baseline to different endpoints. At the end of the study, we expect to

6 measures per participant for T-cell response and antibody level. We will explore the possibility to describe kinetics of these parameters through non-parametric test for comparison of:

- A. *within-the-arm medians* at different times (i.e. baseline vs. either week-2, week-4, week-8, week-12 and week 24) between groups at different follow-up time);
- B. *within the Adults-Cohort medians* at specific time (i.e. Arm-1 vs. either Arm-2 or Arm-3 at baseline, week-2, week-4, week-8, week-12 or week-24).
- C. *within the Elderlies-Cohort medians* at specific time (i.e. Arm-4 vs. either Arm-5 or Arm-6 at baseline, week-2, week-4, week-8, week-12 or week-24).
- D. *Across the cohort medians at specific time* (i.e. Arm-1 vs. Arm-4; Arm-2 vs Arm-5; Arm-3 vs. Arm-6 at baseline, week-2, week-4, week-8, week-12 or week-24)

Explorative kinetics model based on regression techniques for correlated measures will be carried out if normal distribution of data is proven.

11. Data Management

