### 4.2 General Presentation Considerations

The overall outline of the scheduled assessment and other study procedures can be found in the Schedule of Assessment, [Table 5](#). In the following, the data handling conventions should be interpreted within the framework of the Schedule of Assessment.

The date of Enrolment Visit (Time 0) is defined as Day 1. All other study days will be labeled relative to Day 1.

- For observation/event dates on or after Day 1, study day for an observation/event date is derived as:  
Observation/event date – visit Time 0 date + 1 day, which could be Day 1, Day 2, Day 3, etc.
- For observation/event dates prior to Day 1, study day for an event date is derived as:  
Observation/event date – visit Time 0, which could be Day -1, Day -2, etc., referring to 1 day, 2 days, etc., prior to Day 1, respectively.
- Day 0 is not defined.

Baseline is considered as the result of last non-missing evaluation before vaccine administration, unless specified otherwise.

End of Study is defined as the last available post-treatment assessment.

Continuous data will be summarized in terms of the mean, standard deviation (SD), median, minimum, maximum and number of observations, unless otherwise stated.

Count data will be summarized in terms of the median, lower and upper quartile, minimum, maximum and number of observations, unless otherwise stated. Geometric mean titer will be provided also for result in titer.

Categorical data will be summarized in terms of the number of subjects providing data at the relevant time point (n), frequency counts and percentages. Any planned collapsing of categories will be detailed in the SAP text and the data displays.

The minimum and maximum will be reported to the same number of decimal places as the raw data recorded in the database. The mean, median, lower quartile and upper quartile will be reported to one more decimal place than the raw data recorded in the database. The SD will be reported to two more decimal places than the raw data recorded in the database. In general, the maximum number of decimal places reported shall be four for any summary statistic. Confidence intervals will be presented to one more decimal place than the raw data.

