#### 4.13 Determination of Sample Size

No formal testing of hypotheses has been planned for this study. Therefore, no formal sample size calculations were performed. 45 subjects are considered to be adequate to analyze the study objectives.

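### SAP 4.10 gives no between-group estimate or interval for immunogenicity, although protocol 10.2 makes that difference the primary immunogenicity analysis and the deliveries rest dose and age decisions on it

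*SAP*

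**What the plan says.** **Protocol.** Section 10.2 states: "The primary analysis for immunogenicity will be to assess the difference in magnitude of SARS-CoV-2 specific T-cell and antibody responses between the groups". It calls the study descriptive and aims at estimation rather than formal significance. It introduces the detailed contrasts tentatively: "We will explore the possibility to describe kinetics of these parameters through non-parametric test for comparison of" medians within arm over time, between doses within each age cohort, and between dose-matched arms across cohorts. The adult dose contrasts are "Arm-1 vs. either Arm-2 or Arm-3 at baseline" and at five later visits; Arm-2 v Arm-3 is not listed, and nor is Arm-5 v Arm-6. A regression model for correlated measures is allowed only "if normal distribution of data is proven". Section 4.2.3 lists within- and across-cohort comparisons among the exploratory endpoints.

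**SAP, purpose.** Section 1, following protocol 4.2.5, says the immunogenicity analyses at Deliveries 1 and 2 are meant to identify the dose for phase 2/3. Delivery 2 item c also promises an adult-elderly comparison to define the dose for each population.

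**SAP, method.** Section 4.10 provides summaries by visit and arm, category counts and three kinds of graph, introduced by "To visualize the comparison between treatment groups the following graphs will be presented". Section 4.13 says: "No formal testing of hypotheses has been planned for this study". For anti-S, "Results of anti-S-Ab concentration will be summarized descriptively as indicated in Section 4.2", and that section reads: "Continuous data will be summarized in terms of the mean, standard deviation (SD), median, minimum, maximum and number of observations". Geometric means are specified for titres only. Confidence intervals appear only in a decimal-place rule in 4.2. Table 3 and section 4.14 restrict the second interim analysis to Arms 4-6. Section 4.15 declares one change, the added liver analyses.

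**The concern.** The protocol names an analysis, the SAP implements none of it, and the section meant for such changes does not mention it. The result is used: both interim reports are to guide a dose choice, and the second is to compare age groups. Someone choosing a dose would have six columns of per-arm figures and some plots. Nothing would say how large a difference between two 15-person arms is, or how uncertain.

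The anti-S summary adds a problem of scale. Antibody concentrations are usually right-skewed and differences between doses are naturally read as ratios. The SAP accepts this in part, since it plots anti-S on a semi-logarithmic axis, and the protocol's mouse figures (3.5.2) use geometric means. Yet the tabulated mean and SD are arithmetic, and the SAP does not say that the plotted mean is geometric.

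**Working it through.** **1. Is there a planned figure to reproduce?** Only the sample size: 6 arms x 15 = 90, as stated. The documents give no SD, effect size, alpha, power or target precision for any immunogenicity comparison.

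**2. What the protocol lists and what the SAP specifies.** Between-group contrasts in protocol 10.2 for a marker measured at six time points (anti-S, ELISpot):
- adults, Arm-1 v Arm-2 and Arm-1 v Arm-3: 2 x 6 = 12
- elderlies, Arm-4 v Arm-5 and Arm-4 v Arm-6: 2 x 6 = 12
- across age, three dose-matched pairs: 3 x 6 = 18
- total 42, of which 7 are at baseline and 35 are post-vaccination

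Neutralisation is scheduled in the SAP at week 4 and week 24 only, so its count is (2 + 2 + 3) x 2 = 14. SAP 4.10 specifies none of the 42 or the 14.

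**3. Can Delivery 2 item c be produced?** It needs adult and elderly data together. Table 3 shows only Arms 4, 5 and 6 for the second interim analysis, and 4.14 uses only data from those arms. All six arms appear together only at the final analysis, again without a contrast.

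**4. Precision of the missing estimate.** Assumption: log10 SD 0.3 to 0.5, equal in all arms, with all 15 participants per arm evaluable. For two arms, the 95% half-width on the log10 scale is t(0.975, 28) x SD x sqrt(2/15) = 2.048 x 0.365 x SD = 0.748 x SD.

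| log10 SD | half-width | ratio divided/multiplied by |
|---|---|---|
| 0.3 | 0.224 | 1.68 |
| 0.4 | 0.299 | 1.99 |
| 0.5 | 0.374 | 2.37 |

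For the dose-stratified elderly/adult ratio (mean of three arm-pair differences, pooled SD, 6 x 14 = 84 df), the half-width is 1.989 x SD x sqrt(2/45) = 0.419 x SD. The factor is 1.34 at SD 0.3 and 1.62 at SD 0.5.

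**5. What the arithmetic scale does.** If values are log-normal with s = SD x ln 10, the arithmetic mean is exp(s²/2) times the geometric mean: 1.27, 1.53 and 1.94 at SD 0.3, 0.4 and 0.5. Two arms with the same geometric mean but log10 SDs of 0.5 and 0.3 would differ by 1.94/1.27 = 1.53-fold in arithmetic mean. So a gap between arithmetic means can reflect spread alone.

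**The case against.** The strongest reply is that the trial is descriptive. Safety is the primary objective, the comparisons also appear among the exploratory endpoints, protocol 10.2 disclaims formal significance and only explores the tests, and SAP 4.13 is consistent with that. This stands as far as p-values go: their absence is not a fault. It does not excuse the absence of an estimated difference, since the protocol's stated aim is estimation and its primary immunogenicity analysis is a difference.

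Second, per-arm information is substantial: anti-S medians, response percentages, individual profiles on a log axis, neutralisation GMTs, and box-and-scatter plots. This also stands. A reader might infer that dose choice would rest on a mean driven by one or two high responders; the documents do not support that, because medians and individual data are shown. What is missing is the contrast and any interval.

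Third, outputs are defined in a separate TLF specification that was not supplied, and adult week-4 results will be in the first interim report. Both may be true, but the SAP should define the estimates, and placing two reports side by side is not a specified comparison.

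Three stronger readings should also be set aside:
- *The arithmetic scale costs a planned test much of its power.* No document plans a t-test on raw values. The protocol's rank tests are unaffected by log transformation; in simulation with 15 per arm they have about 77% power where a log-scale t-test has 80%.
- *The protocol's many contrasts imply a stated number of false positives.* The SAP runs none of them. The full list also includes 30 within-arm comparisons with baseline (6 arms x 5 visits), where no change is implausible, and the neutralisation list is shorter.
- *A dose-trend model would be much more precise.* Within a cohort with equally spaced log doses and equal arms, the slope per doubling is half the highest-v-lowest dose difference, which the protocol already lists.

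**Conclusion.** The concern holds in a limited form. The SAP leaves out the between-group estimates that protocol 10.2 makes the primary analysis of a secondary objective, attaches no interval to any immunogenicity quantity, gives anti-S no geometric mean, and does not declare the departure. Delivery 2's age comparison has neither a method nor adult data at the second interim analysis. These points follow from the text and need no assumption.

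The size does rest on assumptions: log10 SD 0.3 to 0.5 and complete arms. On that basis a two-arm ratio carries a factor of about 1.7 to 2.4 either way, and the stratified age ratio about 1.3 to 1.6. Intervals widen further if participants are lost or excluded after infection or outside vaccination, as 4.10 requires. A twofold difference between arms could therefore be well within uncertainty, which readers choosing a dose should see. It does not follow that the trial's primary analysis has been lost, since that is safety, or that formal testing is needed. The change should be made; it does not threaten the trial's validity.

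**What to change.** 1. In SAP 4.10, report geometric mean concentration (anti-S) and geometric mean titre (neutralisation) with 95% CIs by arm and visit. The existing substitutions (1.9 and 5) keep the logs defined. Keep the medians, and state which mean is plotted.
2. At week 4 for antibodies and week 2 for ELISpot (4.14 already uses week 4 for neutralisation and week 2 for ELISpot at the interims), report geometric mean ratios with 95% CIs for the dose pairs within each cohort, including Arm-2 v Arm-3 and Arm-5 v Arm-6, and for the dose-matched or dose-stratified elderly/adult contrast. Hodges-Lehmann shifts with CIs are an alternative, for example for ELISpot, where zeros are possible.
3. Label these descriptive, and omit between-arm tests at baseline.
4. Amend Table 3 and 4.14 so that the second interim comparison includes the adult arms' week 2 and week 4 data.
5. Record the change from protocol 10.2 in 4.15. If an interim report has already been issued, add the estimates to the final analysis and say when they were specified.

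A log-dose trend or repeated-measures model is optional. The cost is SAP text and a few tables from data already collected. The drawback is that the intervals will look wide, which is accurate for arms of 15.

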14.2. T cell Immunology

To test the ability of vaccine to induce a T cell response, we will quantify and characterize SARS-CoV-2 specific T cells before and after vaccination by ELISpot and multiparametric flow cytometry. Peripheral Blood Mononuclear Cells (PBMC) will be isolated by density gradient centrifugation, counted and resuspended in culture medium supplemented with 10% heat inactivated FBS.

The first immunogenicity analysis will be performed after 2 weeks from vaccination (T2) using fresh isolated PBMC. Specifically, fresh PBMC isolated from peripheral blood of vaccinated subjects at T2 will be stimulated for 18-24 hours with SARS-CoV-2 peptides mix (designed on the S-protein protein) and the IFN- β production by single cells will be evaluated by ELISpot assay. Results will be expressed as Spot Forming Cells (SFC) per million of PBMC.

Moreover, the kinetic of T cell induction after vaccination will be evaluated on frozen PBMC using different T cell assays (ELISpot assay, intracellular staining/flow cytometry and Tetramer staining) with the aim to deeply characterize the vaccine-induced T cell response overtime. Specifically, the ELISpot assay and the intracellular staining/flow cytometry will be performed after in vitro stimulation with S-protein-specific peptides and allow defining the functionality/polyfunctionality (IFN- γ , TNF- α , IL-17, IL-2, IL-10, CD107a) of antigen specific T cell clones. The results of the intracellular staining will be expressed as frequency of specific T cells able to exert one (single functional), two (double-functional), three (triple-functional) or four (quadruple-functional) different functions. Moreover, the Tetramer staining and flow cytometry will allow an ex vivo deep characterization of S-protein-specific T cells to define their phenotype (activated, exhausted, effector, memory).

15. Ethical issues

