### 3.2.2 Immunogenicity Variables

- Antibodies to SARS-CoV-2 S-protein (anti-S-Ab)
- Antibodies to SARS-CoV-2 N-protein(anti-N-Ab)
- SARS-CoV-2 micro-neutralization assay
- Magnitude of interferon gamma (IFN $\gamma$ ) ELISpot response (SFC/10 $^6$  PBMC)
- T-cell response (number of positive spike pools-only applicable for fresh PBMC at week 2)

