#### 4.14 Interim Analyses

There will be two interim analyses (IAs) before general database lock and provision of final study results.

Each interim analyses will be preceded by a DRM focusing on the subjects to be included in the actual IA, i.e. for the first interim analysis (Deliverable 1) the target subject pool will be those who were enrolled for Arm 1 – 3 (Adults), for the second interim analysis (Deliverable 2) the target pool will be those who were enrolled for Arm 4 – 6 (Elderlies).

The first interim analysis will use data collected in Arm 1 – 3 up to the last subject in Arm-3 completed its Week 4 visit (Adults, highest dose). The second interim analysis will use data collected in Arm 4 – 6 up to last subject in Arm-6 completed its Week 4 visit (Elderlies, highest dose).

All outputs specified in the study's TLF Specification will be provided for both IAs. Grouping of IA summaries will follow guidelines specified in Section 4.2.1.

Selected immunogenicity endpoints such as ELISpot and nAb data will be analyzed at single timepoints during interim analyses. Results of ELISpot and nAb will be reported only for Week 2 and Week 4, respectively.

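### The SAP's T-cell response rate is positivity at Week 2, not vaccine-induced response, because the rule does not use the subject's own T0 ELISpot

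*SAP*

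**What the plan says.** **The rule.** SAP section 3.2.2 lists the variable as "T-cell response (number of positive spike pools-only applicable for fresh PBMC at week 2". Section 4.10 turns the pool count into two categories: "Result will be negative if number of positive pools is zero and positive if number of positive is greater than or equal to one". Neither section refers to T0.

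**The protocol's aim.** Protocol section 10.2 states: "We will assess vaccine immunogenicity by comparing the change in these immunological parameters from baseline to different endpoints". Section 14.2 sets out to "quantify and characterize SARS-CoV-2 specific T cells before and after vaccination by ELISpot". ELISpot is marked at T0 in both schedules (Protocol Figure 9, SAP Table 5).

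**Fresh and frozen cells.** Protocol section 14.2 says "The first immunogenicity analysis will be performed after 2 weeks from vaccination (T2) using fresh isolated PBMC", and that "the kinetic of T cell induction after vaccination will be evaluated on frozen PBMC using different T cell assays". SAP section 4.10, as revised in version 4.0, adds that "ELISpot assay results on frozen PBMC samples obtained on Week 2, will be provided by the sponsor" from outside the EDC system, to be analysed together with the EDC results.

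**The interims.** SAP section 4.14 says "Results of ELISpot and nAb will be reported only for Week 2 and Week 4, respectively". SAP section 1 gives the choice of a phase 2/3 dose as an aim of the preliminary immunogenicity analysis at both interims.

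**The concern.** A rate called T-cell response will be read as the share of subjects in whom the vaccine induced a response. As defined, it is the share with a positive pool two weeks after vaccination, whatever their status before.

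Nothing else in the design removes the difference. There is no unvaccinated arm. Protocol section 6.5 excludes antibody-positive subjects and reported COVID-19 cases, which lowers the chance of pre-existing spike-reactive T cells but does not rule it out. The T0 sample that would settle the matter is scheduled. SAP sections 4.11.3 and 4.11.5 specify change from baseline for laboratory values and vital signs, but section 4.10 specifies none for ELISpot. Because the interims show ELISpot at Week 2 only, their readers would have no T0 figure beside it.

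The secondary concern is that two Week 2 ELISpot values will exist, one fresh and one frozen, and the SAP does not say which fills the Week 2 position in the by-visit summaries and box-and-scatter plots.

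**Working it through.** **1. Check of the plan's own figure.** Protocol section 10.2 expects six T-cell measures per participant. The scheduled ELISpot visits are T0, W2, W4, W8, W12 and W24, which is six, so the figure reproduces and includes T0. The positivity rule uses one of the six, fresh W2.

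**2. Effect on the reported rate.** Let p be the true vaccine-induced rate and q the share already positive at T0. Assume that the two are independent and that baseline positivity persists to Week 2. The documents give neither p nor q, so both are assumed ranges.

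Reported rate = p + (1 − p)q

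| q (assumed) | True 50% | True 70% | True 90% |
|---|---|---|---|
| 5% | 0.50 + 0.50 × 0.05 = 52.5% | 0.70 + 0.30 × 0.05 = 71.5% | 90.5% |
| 10% | 55% | 73% | 91% |
| 20% | 60% | 76% | 92% |

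**3. Numbers per arm (n = 15).** Expected T0-positive subjects are 15q = 0.75, 1.5 or 3.0. The chance of at least one in an arm, 1 − (1 − q)^15, is 54%, 79% or 96%. Some of these subjects would have responded anyway, so the expected extra positives are 15(1 − p)q. At p = 50% that is 0.375, 0.75 or 1.5 subjects.

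**4. Effect on a dose comparison.** With the same q in both arms, the reported difference is (p₂ − p₁)(1 − q). For 70% against 50%:

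- q = 5%: 20 × 0.95 = 19 points
- q = 10%: 20 × 0.90 = 18 points
- q = 20%: 20 × 0.80 = 16 points

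The expected ranking is unchanged. If q differs between arms, or between adults and elderly subjects, that protection is lost.

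**5. Fresh against frozen.** The documents give no bridging between cell types. If frozen cells kept 50% to 90% of the fresh signal (assumption), a frozen T0 set against a fresh W2 would inflate the fold-rise by 1/0.9 = 1.11 to 1/0.5 = 2.0. A fresh W2 followed by a frozen W4 would show a false fall of 10% to 50%. This arises only if the two cell types are placed in one series.

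**The case against.** Several points on the other side have force.

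- **Baseline is not ignored overall.** Protocol section 10.2 plans within-arm comparisons with baseline, and SAP section 4.10 summarises each immunogenicity endpoint by visit. T0 magnitude by arm should therefore appear at the final analysis. This stands. What is missing is T0 in the positivity rule and T0 positivity by arm.
- **The protocol already assigns kinetics to frozen cells, and the added frozen Week 2 data make an all-frozen series possible.** This stands, and it reduces the second limb to a missing selection rule. A reader might infer that the kinetics are confounded as planned. The documents support only that the SAP does not prevent mixing.
- **Cell status is partly inferred.** A reader might state as fact that no fresh T0 assay exists and that the interim Week 2 result is on fresh cells. Neither is written. Both schedules mark T0 without cell type, SAP section 4.14 names none, and Protocol Figures 6 and 7, which colour-code fresh and frozen sampling, are not shown in the available text. Protocol section 14.2 and SAP section 3.2.2 make both fair inferences and no more.
- **The size is assumed and small against sampling error.** With 8 of 15 positive, the exact 95% interval is 27% to 79%, and SAP section 4.13 plans no formal testing. This stands. However, the shift has a known direction, and adding subjects under the same rule would not remove it.

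**Conclusion.** The point holds as a matter of definition. The SAP's T-cell response is Week 2 positivity unadjusted for T0, and any pre-existing spike reactivity is counted as response to vaccine. This conclusion does not depend on the cell type used at T0.

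Its size cannot be fixed from the documents. Under an assumed 5% to 20% T0 positivity, independent of vaccine response and lasting to Week 2, the overstatement is 2.5 to 10 points at a true 50%, 1.5 to 6 points at a true 70%, and 0.5 to 2 points at a true 90%.

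A reader might go further and infer that the dose choice would be wrong. The documents do not support that. They do not name T-cell positivity as the selection criterion, and equal baseline positivity across arms shrinks a difference without reversing its expected order. The absolute rate is affected more than the ranking.

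Mixing of fresh and frozen Week 2 values is a possibility left open by SAP version 4.0, and it runs against the intent of Protocol section 14.2. The point is worth fixing because the remedy is cheap and relies on scheduled T0 samples and Week 2 results already due from the sponsor.

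**What to change.** Amend SAP section 4.10 as follows.

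1. Label the fresh Week 2 result *positive at Week 2* wherever it is reported, including the interim reports.
2. At the final analysis, define a T-cell responder on paired frozen T0 and Week 2 PBMC as positive at Week 2 and negative at T0. Apply the laboratory's same pool-positivity criterion to both samples and fix it before the analysis. Tabulate T0 positivity by arm.
3. Name the denominator. Under the assumptions above, at p = 50% and q = 20%, dividing by all paired subjects gives 0.8 × 50% = 40%, and dividing by those negative at T0 gives 50%.
4. Use frozen PBMC values only for change from baseline and for by-visit ELISpot summaries and plots, in line with Protocol section 14.2. Show fresh Week 2 separately.

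**Cost.** This needs SAP wording, one extra table and one criterion to document, since the present rule covers fresh Week 2 cells only. No new visit or blood draw is needed, but T0 and Week 2 must both be available as frozen ELISpot results; the SAP states this for Week 2 only. The reported response rate will be slightly lower, and the interim ELISpot figures will carry a caveat.
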